**Statistical analysis plan (SAP) for the (cost-)effectiveness of:
an innovative, personalised intervention of therapeutic Virtual
Reality (VR) IntEgrated within physioTherapY for a subgroup of
complex chronic low back pain (CLBP) patients (VARIETY-study)**

Publication date: 27-01-2023

Sponsor: ZonMw (10270032021502)

Document version: 1.0

Trial registration: ClinicalTrials.gov (ID: NCT05701891)

Main applicant:

[name], HAN

Principal investigator:

[name], HAN

Co-applicants:

[name], VU

[name] [name], Maastricht University

[name] [name], HAN

[name] [name], Radboudumc

[name] [name], Radboudumc

Study objectives and outcomes

Main objective

- To evaluate the effectiveness of physiotherapy with integrated multimodal VR for patients with complex CLBP, compared to usual primary physiotherapy care on physical functioning evaluated by the Oswestry Disability Index (ODI) at 3 months (primary end-point) and 12 months follow-up.

Secondary objective

- To evaluate the effectiveness of physiotherapy with integrated multimodal VR for patients with complex CLBP, compared to usual primary physiotherapy care on secondary outcome measures pain intensity, pain related fears, pain self-efficacy, physical activity level, global perceived effect and problems with activities at 3 months (primary end-point) and 12 months follow-up.
- To evaluate the cost-effectiveness of physiotherapy with integrated multimodal VR for patients with complex CLBP, compared to usual primary physiotherapy care for the 12-month period.

Trial methods

Design

- This study is a pragmatic, multicenter, two-arm, parallel, superiority, cluster-randomized controlled trial. Outcome variables will be measured at baseline, after 1 month (T1; during treatment), 3 months (T3; directly post-treatment), 6 months (T6; 3 months post-treatment) and 12 months (T12; 9 months post-treatment) follow-up, as described in table 1.

Randomization

- Eligible physiotherapists will be randomized on practice level using an online software program and stratified for completion of the three-year master to specialize as a psychosomatic physiotherapist.

Allocation

- Patients will be treated by their physiotherapist and follow the intervention their physiotherapist was randomized to.

Blinding

- Patients cannot be blinded, but will only be informed about their own intervention and will neither be informed about the presence of two arms in the trial nor the intervention received in the other arm.

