- Participating patients will be described using the following baseline characteristics: age, sex, BMI, tobacco use, duration of complaints, comorbidities, occupation, education level, diagnostic and therapeutic procedures in past 6 months, medication use and experience with VR for treatment and entertainment, as shown in table 2. Moreover, participants will be described using the following clinical outcome measures: physical functioning, pain intensity, pain related fears, pain self-efficacy, physical activity level, problems with activities and intervention expectations.
- Participating physiotherapists will be described using the following baseline characteristics: age, gender, number of years' experience as a physiotherapist and specialization (i.e. finished with a master's degree), as shown in table 3.

Process evaluation

- The following process parameters regarding the physiotherapy treatment will be monitored by the physiotherapists for both arms: number of sessions, duration of sessions, applied treatment modality per session and adverse events (if applicable).
- In the experimental arm, the following VR related parameters will be additionally monitored using an online dashboard: treatment modality, daily treatment duration and VAS pain score (before and after VR use).

Analysis

Primary analysis

- The primary analysis will be an intention-to-treat, longitudinal mixed-model analysis comparing the effectiveness of physiotherapy with integrated multimodal VR for patients with complex CLBP, compared to usual primary physiotherapy care on physical functioning at 3 months (primary end-point) and 12 months follow-up.
- All participants in this study will be analyzed using mixed-models with maximum likelihood estimation.
- The analysis will be adjusted for important prognostic characteristics that potentially confound the treatment effects (e.g. physical functioning, pain severity, pain-related fears, BMI, tobacco use) and the baseline value of the outcome measure, with addition of other patient and/or physiotherapist characteristics that substantially differ between the two arms at baseline.

Secondary analysis

- Clinical effectiveness on secondary outcome measures:

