- Costs and effect differences will be estimated using Seemingly Unrelated Regression analyses, in which their possible correlation can be accounted for. The 95% confidence intervals surrounding the cost differences will be estimated using Bias-Corrected and Accelerated (BCA) bootstrapping. Subsequently, Incremental Cost-Effectiveness Ratios (ICERs) will be calculated by dividing the differences in costs by the differences in QALYs. Uncertainty surrounding the cost-differences and ICERs will be estimated using bias correct and accelerated (BCA) bootstrapping techniques (5000 replications) and be graphically illustrated by plotting BCA-bootstrapped cost-effect pairs on cost-effectiveness planes. Also, cost-effectiveness acceptability curves will be constructed to provide an indication of the probability of physiotherapy with integrated multimodal VR therapy being cost-effective with usual care at different values of willingness to pay.

Responder analysis

- The proportion of participants with a minimal clinically important difference (MCID), responders, on each of the outcome variables between treatment arms, at 3 months and 12 months follow-up:
 - 8 points improvement on the ODI (Hung et al., 2018)
 - 15% and/or 1-point improvement on the NRS (Salaffi et al., 2004)

Availability of data and materials

- The datasets generated and analyzed during the current study will be available in the Dataverse repository.
- The research protocol is accessible at ClinicalTrials.gov (ID: NCT05701891).

Figure 1. *Flow of participants*

[figure not shown]

Table 1. *Overview of measurements*

	T0	T1	T3	T6	T12
Primary outcome measure					
Oswestry Disability Index (ODI)	X	X	X		X
Secondary outcome measure					
Numeric Rating Scale (NRS)	X	X	X		X
Fear Avoidance Beliefs Questionnaire (FABQ)	X	X	X		X
Pain Catastrophizing Scale (PCS)	X	X	X		X
Physical activity (self-reported)	X	X	X		X
Global perceived effect (GPE)		X	X		X
Patient-specific complaints questionnaire (PSK)	X		X		X
Pain self-efficacy (PSEQ)	X	X	X		X
Credibility and expectancy questionnaire (CEQ)	X	X			
Igroup presence questionnaire (IPQ)		X	X		
Economic parameters					
Quality-adjusted life years (QALY) (EQ-5D-5L)	X		X	X	X
Health-related and work-related costs	X		X	X	X
Patient characteristics	X				
Treatment parameters					
Other treatment than PT because of LBP, in past 12 weeks			X		
Duration of PT-treatment (number of weeks/sessions, reported by PT)			X		

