Content of PT-treatment (usage of treatment modalities, reported by PT)			X		

Table 2. *Baseline characteristics*

	Experimental group (n =)	Control group (n =)
General characteristic		
Age (years), mean \pm SD		
Sex (female (n)), %		
BMI, mean \pm SD		
Smoker (yes), %		
Duration of symptoms (years), mean \pm SD		
Work status		
Paid work (fulltime), %		
Pain work (parttime), %		
Unpaid work, %		
No work, but not retired, %		
Retired, %		
Student, %		
Use of pain medication (yes), %		
Comorbidities affecting daily life (count), %		
Diagnostic procedures for CLBP in past 6 months (yes), %		
Treatment for CLBP in past 6 months (yes), %		
Experience with VR for treatment (yes), %		
Experience with VR for entertainment (yes), %		

Table 3. *Physiotherapist characteristics*

	Experimental group (n =)	Control group (n =)
General characteristic		
Age (years), mean \pm SD		
Sex (female), %		
Years' experience as physiotherapist (years), mean \pm SD		
Specialization		
Manual, %		
Sport, %		
Psychosomatic, %		
Children, %		
Geriatric, %		
Orofacial, %		
Pelvic, %		
Oncology, %		

Table 4. *Primary and secondary outcome measures*

	Exp. (n=)	Control (n=)	Est. diff. between groups	
			Crude (95% CI, p-value)	Adj. (95% CI, p-value)
Primary clinical outcomes				
Physical function (ODI), mean \pm SD				
Baseline				
1 months follow-up				
3 months follow-up				
12 months follow-up				
Secondary clinical outcomes				
Pain intensity (NRS), mean \pm SD				
Baseline				
1 months follow-up				
3 months follow-up				
12 months follow-up				
Pain related fears (FABQ), mean \pm SD				
Baseline				
1 months follow-up				
3 months follow-up				
12 months follow-up				
Pain related fears (PCS), mean \pm SD				
Baseline				
1 months follow-up				
3 months follow-up				
12 months follow-up				
Physical activity, mean \pm SD				
Baseline				
1 months follow-up				
3 months follow-up				
12 months follow-up				
Global perceived effect (at least 'much improved'), %				
3 months follow-up				

	Exp. (n=)	Control (n=)	Est. diff. between groups	
12 months follow-up				
Activity level (PSK)				
Baseline				
3 months follow-up				
Pain self-efficacy (PSEQ), mean \pm SD				
Baseline				
1 months follow-up				
3 months follow-up				
12 months follow-up				
Treatment expectation (CEQ), mean \pm SD				
Baseline				
1 months follow-up				
Sense of presence (IPQ), mean \pm SD				
1 months follow-up				
3 months follow-up				

Table 5: Costs per arm and cost differences across arms

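### The imbalance-driven covariate rule does not exclude baseline treatment expectation (CEQ), which patients very probably rate knowing their own intervention, so the adjusted ODI difference may stop being the total effect

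*SAP*

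**What the plan says.** **Covariate rule.** The SAP's Primary analysis section describes an intention-to-treat mixed model. The named covariates are given only as examples, plus the baseline outcome: "e.g. physical functioning, pain severity, pain-related fears, BMI, tobacco use) and the baseline value of the outcome measure". The sentence goes on: "with addition of other patient and/or physiotherapist characteristics that substantially differ between the two arms at baseline". It gives no closed list, no threshold and no exclusion. Secondary analysis says that the other clinical outcomes are handled in the same way.

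**Where expectation appears.** The section on baseline patient and physiotherapist characteristics ends its list of measures with "physical activity level, problems with activities and intervention expectations". Table 1 schedules the "Credibility and expectancy questionnaire (CEQ") at T0 and T1, in the secondary outcome block. Table 4 has a row "Treatment expectation (CEQ), mean" with baseline and 1-month lines. CEQ is not in Table 2.

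**What patients know.** Randomization is at practice level. Under Allocation, patients "follow the intervention their physiotherapist was randomized to". Under Blinding: "Patients cannot be blinded, but will only be informed about their own intervention and will neither be informed about the presence of two arms".

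**The concern.** A baseline covariate is safe to adjust for when allocation cannot have changed it. A credibility and expectancy score needs a treatment to rate. In this trial that is very probably the one treatment the patient has been offered: physiotherapy with VR in one arm, usual physiotherapy in the other. T0 CEQ is taken before treatment starts, but it may already respond to allocation.

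The rule selects covariates because they differ between arms. If the offer of VR raises expectation, the difference it creates is what triggers the adjustment. A numerical threshold for a substantial difference would not cure this, so the point is distinct from the rule's general openness. The independent statistician, blinded to allocation, has no instruction to leave CEQ out.

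At stake is the meaning of the adjusted column of Table 4, for ODI and for the secondary outcomes. The objective is the whole effect of the VR-integrated package. Holding an allocation-induced expectation constant takes part of that effect away. The shift is towards no difference if VR raises expectation and higher expectation goes with lower ODI.

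**Working it through.** **Inputs from the SAP (Sample size).** Planned difference 10 ODI points, SD 15, 90% power, alpha 0.05, ICC 0.05, 15% drop-out, 60 patients per group, 20 physiotherapists and 120 patients.

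**The plan's own figure.** Patients per physiotherapist = 120/20 = 6, so the design effect is 1 + (6 − 1) × 0.05 = 1.25.
- Two-sided: 48 × 1.25 = 60 before drop-out, and 60/0.85 = 70.6, so 71 after it.
- One-sided: 39 × 1.25 = 48.75, and 48.75/0.85 = 57.4, so 58.

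The stated 60 is thus close to the one-sided result, or equals the two-sided result without drop-out. That is a separate matter. Only the 10 points, the SD of 15 and 60 × 0.85 = 51 completers per arm are used below.

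**Inputs that are assumptions.** The SAP gives neither the arm difference in T0 CEQ (d, in SD units) nor the within-arm CEQ-ODI correlation (r). The ranges used are d = 0.2 to 0.8 and r = 0.1 to 0.4.

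**Step 1: CEQ as the only added covariate.** The adjusted arm difference equals the crude difference minus d times the within-arm ODI slope per SD of CEQ. That slope is r × 15, so the amount removed is d × r × 15.

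**Step 2: baseline ODI also in the model.** The slope must then be taken given baseline ODI. For illustration, assume a correlation of 0.2 between CEQ and baseline ODI and 0.5 between baseline and follow-up ODI, with aligned signs and baseline ODI balanced. The standardised slope is (r − 0.2 × 0.5)/(1 − 0.2²) = (r − 0.1)/0.96. The amount removed is d × 15 × that slope.

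**Step 3: power for the Step 1 cases.** Two-sided, with 51/1.25 = 40.8 effective patients per arm, residual SD 15 × √(1 − r²), and the effective number reduced by the factor 1/(1 + d²/4) because CEQ is correlated with arm. Without CEQ, power for 10 points is 85%.

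| d | r | Removed, Step 1 | Left of 10 | Power | Removed, Step 2 |
|---|---|---|---|---|---|
| 0.2 | 0.1 | 0.3 | 9.7 | 83% | 0 |
| 0.3 | 0.2 | 0.9 | 9.1 | 79% | 0.47 |
| 0.5 | 0.3 | 2.25 | 7.75 | 66% | 1.56 |
| 0.8 | 0.4 | 4.8 | 5.2 | 35% | 3.75 |

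Middle case: 0.5 × 0.3 × 15 = 2.25 in Step 1; 0.5 × 15 × 0.2/0.96 = 1.56 in Step 2.

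**Check by simulation.** Twenty clusters of 6, true total effect −10, d = 0.5, r = 0.3, no baseline ODI: the mean estimate was −9.97 without CEQ and −7.72 with it, in line with Step 1.

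**The case against.** Much of the opposing case stands.

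- **Classification.** Expectation is listed with the clinical outcome measures, not with the characteristics that feed Table 2, and Tables 1 and 4 treat it as a secondary outcome. A reader might infer that CEQ will enter the model. The SAP does not say so; it only fails to exclude it. Being an outcome is no protection, though: functioning, pain and fears are outcomes too and are named as covariates.
- **Timing.** The SAP does not state whether T0 CEQ comes before or after disclosure. That it follows disclosure is an inference, though a strong one, since the patient must have some treatment to rate and learns of only one.
- **Other sources of imbalance.** Unblinded physiotherapists screen patients after their practice is randomised, so a CEQ difference could partly reflect who was recruited. Adjusting for that part would reduce bias. The formula assigns the whole difference to allocation.
- **Size of the difference.** Control patients do not know of a VR arm, which limits disappointment. Nothing in the SAP shows that the arms will differ on CEQ.
- **Crude estimates.** Table 4 reports crude and adjusted differences side by side, so a shift would be visible. This softens the problem but does not remove it, because the primary analysis is the adjusted model.
- **Costs.** A reader might extend the point to the cost regressions. The footnote to Table 5 gives their adjustment set, and CEQ is not in it.

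**Conclusion.** The concern holds in a limited form. The covariate rule leaves open the adjustment of the primary and secondary effectiveness models for a rating that allocation has very probably influenced. If that happens, and the imbalance comes from allocation, the adjusted difference no longer estimates the total effect that the objective asks for.

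The size cannot be determined from the SAP. Under the assumed ranges about 0.3 to 4.8 ODI points are removed, and less with baseline ODI in the model (about 1.6 instead of 2.25 in the middle case). The middle case of Step 1 is 2.25/10, or about 22%, of the planned effect, and one might be tempted to quote that as the expected loss. The documents do not support this: d and r are assumed, the figure ignores baseline ODI, and it attributes the entire imbalance to allocation. The power figures carry the same limits.

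It is worth correcting before database lock because the remedy is simple and the rule, as worded, favours selection of the variable when the offer of VR has moved it.

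**What to change.** Add to the Primary analysis section, with effect for the secondary effectiveness outcomes: CEQ at T0 and T1 is not a covariate in these models; it is reported descriptively by arm; any CEQ-adjusted model is labelled exploratory. It would also help to state whether T0 CEQ is completed before or after the patient is told the intervention.

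The Table 5 adjustment set needs no change, and CEQ may stay in the imputation models. A general ban on every measure that knowledge of the arm might influence is not advisable, since in an unblinded trial it could exclude useful baseline measures such as ODI itself.

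The cost is a short addition to the SAP and the loss of a possibly prognostic covariate that might also capture some differential recruitment. Baseline ODI, pain, fears and prior VR experience remain available for that purpose.

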- Blinding of participating physiotherapists is not possible, due to the nature of the intervention.
- Blinding of coordinating researchers is not possible, as they need information about treatment allocation for adequate study coordination.
- Blinding of the analyses will be achieved by an independent statistician blinded for treatment allocation, who will perform the primary study analyses.

Sample size

- A clinically relevant between-group difference of at least 10 points on the ODI after 3-months follow-up is expected, which seems plausible based on recent pilot studies with VR from our research group and others. For this expected and clinically relevant difference of 10 and a standard deviation of 15, 60 patients are needed per group ($\alpha=0.05$; power=90%; ICC for clusters 0.05; 15% drop-out). We expect to include 1 patient every 2 months per physiotherapist. A total of 20 participating physiotherapists will result in a total of 120 patients after 12 months.

Time schedule

- This study will start in the first quarter of 2023. Data collection will last until the first quarter of 2025.
- Approval from the medical-ethical committee (METC Oost-Nederland) was granted (case number: 2022-15794).
- The trial was registered with ClinicalTrials.gov (ID: NCT05701891).

Statistical principles

- All analyses in this plan are a priori analyses in that they have been defined in the protocol.
- All outcomes are analyzed for superiority of the experimental group in favor of the control group.
- All analyses described in the plan will take place after database locking, which will occur once all participants have finished their final measurement. An independent statistician that will be blinded for allocation will perform the main analyses.
- All statistical tests will be two-sided and the nominal p-value will be reported. All confidence intervals presented will be 95% and two-sided. The assumption of normal distribution will be checked by visual inspection of Q-Q plots. For skewed data, the interquartile range will be reported.
- Statistical significance is claimed if the null hypothesis is rejected at the significance level (alpha) of $p \leq 0.05$ (one-sided).
- Continuous variables will be summarized by means and SDs in case of a normal distribution and by median and interquartile range in case of a skewed distribution.
- Categorical variables will be summarized by frequencies and percentages.

Hypotheses

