 - The secondary effectiveness analysis will be performed similarly as the primary effectiveness analysis: an intention-to-treat, mixed-model analysis, to evaluate the effectiveness of physiotherapy with integrated multimodal VR for patients with complex CLBP, compared to usual primary physiotherapy care on pain intensity, pain related fears, pain self-efficacy and problems with activities at 3 months (primary end-point) and 12 months follow-up.

Cost-effectiveness

- Health-related Quality of Life: At baseline, 3, 6, and 12 months after start of the intervention, the participants' health states were assessed using the EuroQol 5D Health Questionnaire 3-level version (EQ-5D-5L). Using the Dutch EQ-5D-5L tariff, these health states were converted into utility values (0=dead; 1=full health). Quality-adjusted life-years (QALYs) were calculated using the area under the curve approach.
- Costs: In line with Dutch guidelines, costs were assessed from a societal perspective, meaning that all costs were included irrespective of who paid or benefited.

- Data on other healthcare utilization, informal care, unpaid productivity, and absenteeism. For the cost-utility and -effectiveness analyses, all participants included in the study will be analyzed, with missing data handled by using Multivariate Imputation by Chained Equations (MICE) and the number of imputed datasets will be determined using the loss of efficiency approach. Imputation models will include all available cost and effect measure values as well as variables differing between groups at baseline, variables related to the “missingness” of data and variables related to the outcomes. Pooled estimates will be calculated using Rubin’s rules.

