Costs during 12-month follow-up period*	Experimental group (n=), mean costs in € (SE)	Control group (n=), mean costs in € (SE)	Crude mean cost difference in € (SE)	Adjusted* mean cost difference in € (SE)
Intervention-related costs				
Primary health care costs (other than intervention) ^a				
Secondary health care costs ^b				
Medication costs ^c				
Presenteeism costs				
Absenteeism costs				
Unpaid productivity costs				
Informal care costs				
Total costs				

SE = standard error, CI = confidence interval.

*adjusted for treatment arm, baseline costs, QALY, work status, gender, age

- a. primary health care, other than the (experimental or control) intervention (e.g., general practitioner, acupuncturist);
- b. secondary health care (e.g., hospital, rehabilitation center);
- c. (prescribed and over-the-counter) medication for low back pain.

Table 6. *Cost-effectiveness analysis*

Analysis	Sample size		Outcome	ΔC (95 % CI)	ΔE (95 % CI)	ICER	Distribution CE-plane (%)			
	EXP	CON		€	Points		€/point	NE ^a	SE ^b	SW ^c
Main analysis— imputed dataset			ODI (0-100)							
			NRS pain (0-10)							
			QALYs (range: 0–1)							
SA1—health care perspective			ODI (0-100)							
			NRS pain (0-10)							
			QALYs (range: 0–1)							
SA2—human capital approach			ODI (0-100)							
			NRS pain (0-10)							
			QALYs (range: 0–1)							
SA3—complete cases for cost outcomes only			ODI (0-100)							
			NRS pain (0-10)							

Analysis	Sample size		Outcome	ΔC (95 % CI)	ΔE (95 % CI)	ICER	Distribution CE-plane (%)			
	EXP	CON		€	Points	€/point	NE ^a	SE ^b	SW ^c	NW ^d
			QALYs (range: 0–1)							
SA4-a – per protocol cases only (excluding major protocol violators only)			ODI (0-100)							
			NRS pain (0-10)							
			QALYs (range: 0–1)							
SA4-b– per protocol cases only (excluding major and minor protocol violators)			ODI (0-100)							
			NRS pain (0-10)							
			QALYs (range: 0–1)

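### Practices are randomised, but no analysis states a practice term: the economic methods omit between-practice variance and the primary model's random effects are left open

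*SAP*

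**What the plan says.** Under Randomization the SAP states: "Eligible physiotherapists will be randomized on practice level using an online software program". The Sample size item arrives at 60 patients per group using "power=90%; ICC for clusters 0.05; 15% drop-out", and expects 120 patients from 20 physiotherapists.

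The Primary analysis is an intention-to-treat longitudinal mixed model: "All participants in this study will be analyzed using mixed-models with maximum likelihood estimation". Prognostic covariates are listed, and patient or physiotherapist characteristics that differ at baseline may be added. No random effect is named for patient, physiotherapist or practice, and no degrees-of-freedom method is given. Secondary outcomes follow the same approach.

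Under Cost-effectiveness: "Costs and effect differences will be estimated using Seemingly Unrelated Regression analyses, in which their possible correlation can be accounted for". Then: "The 95% confidence intervals surrounding the cost differences will be estimated using Bias-Corrected and Accelerated (BCA) bootstrapping". The bootstrap has 5000 replications and is stated for cost differences, ICERs and the plotted cost-effect pairs. The unit to be resampled is not stated. On missing data: "Imputation models will include all available cost and effect measure values as well as variables differing between groups at baseline", plus variables related to missingness and to the outcomes. The Table 5 footnote describes the cost differences as "adjusted for treatment arm, baseline costs, QALY, work status, gender, age".

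**The concern.** The design and sample size treat patients of one practice as correlated, and the trial enrols extra patients for that reason. The analysis sections do not say how that correlation enters the inference.

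The economic analysis is the clearer case, because its method is named. Seemingly unrelated regression in its standard form treats patients as independent and links only the two equations. Confidence intervals for costs and effects, cost-effectiveness planes and acceptability curves would then look more certain than the design allows.

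For the primary endpoint the gap is one of specification. A longitudinal mixed model may carry a practice intercept or only patient-level effects. The statistician who runs the main analyses could choose either, and the second choice raises the type I error. Even with a practice intercept, there are at most 20 practices, so the reference distribution matters.

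**Working it through.** **Inputs.** From the SAP's Sample size item: difference 10, SD 15, alpha 0.05, power 90%, ICC 0.05, drop-out 15%, 120 patients, 20 physiotherapists. The number of practices is not given. Randomisation by practice means at most 20 clusters, so the mean cluster size m is at least 120/20 = 6. Ten practices of 12 (10×12) is an assumption used as a second scenario beside 20×6.

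**The plan's own figure.** n per group = 2 × [15 × (z_alpha + 1.282)/10]², and the design effect is DE = 1 + (m − 1) × ICC = 1 + 5 × 0.05 = 1.25.
- Two-sided: 47.3, so 48. 48 × 1.25 = 60. With drop-out, 60/0.85 = 70.6, so 71.
- One-sided: 38.5, so 39. 39 × 1.25 = 48.75. With drop-out, 48.75/0.85 = 57.4, so 58.

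At m = 6, the stated 60 is matched two-sided without drop-out and nearly matched one-sided with it. Which route was taken is a separate question. Either way, the design effect is part of the size.

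**If practice is ignored.** The naive standard error is 1/√DE of the correct one. Type I error is from simulation of a balanced two-arm trial at one time point without covariates (200,000 trials per cell, two-sided 5%).

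| ICC | DE, m=6 | SE too small by | Error, 20×6 | DE, m=12 | SE too small by | Error, 10×12 |
|---|---|---|---|---|---|---|
| 0.01 | 1.05 | 2.4% | 5.6% | 1.11 | 5.1% | 6.2% |
| 0.02 | 1.10 | 4.7% | 6.2% | 1.22 | 9.5% | 7.6% |
| 0.05 | 1.25 | 10.6% | 8.0% | 1.55 | 19.7% | 11.7% |
| 0.10 | 1.50 | 18.4% | 11.0% | 2.10 | 31.0% | 18.1% |

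The formula 2 × [1 − Φ(1.96/√DE)] at ICC 0.05 gives 8.0% and 11.5%. The SAP also states a one-sided 5% rule. On that reading 1 − Φ(1.645/√DE) gives 7.1% and 9.3%.

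**If a practice intercept is fitted (ICC 0.05).** K is the number of practices.

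| Estimator and reference | 20×6 | 10×12 |
|---|---|---|
| ML, normal | 6.5% | 8.7% |
| REML, normal | 5.6% | 6.8% |
| ML, t on K−2 df | 4.9% | 4.6% |
| REML, t on K−2 df | 4.2% | 3.5% |

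Changing the reference moves ML by 1.6 and 4.0 points (6.47 to 4.85; 8.67 to 4.64). Changing ML to REML with a normal reference moves it by about 0.9 and 1.9 points (6.47 to 5.62; 8.67 to 6.80). The degrees of freedom therefore matter more than the estimator.

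**Economic intervals.** Simulated coverage of nominal 95% intervals at ICC 0.05 (3,000 trials, 1,000 resamples, Monte Carlo error about 1 point). Skewed residuals are gamma with shape 1.

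| Method | Normal 20×6 | Skewed 20×6 | Normal 10×12 | Skewed 10×12 |
|---|---|---|---|---|
| Patients resampled, BCA | 91.3% | 90.2% | 86.6% | 86.2% |
| Practices resampled, percentile | 91.7% | 91.8% | 86.9% | 88.0% |
| Two-stage with shrinkage | 94.9% | 95.5% | 93.6% | 94.1% |
| Practice-level SE, t on K−2 df | 94.8% | 95.2% | 94.9% | 95.1% |

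At ICC 0 the patient-level BCA interval covers 94.3% and 94.9% (normal, 20×6 and 10×12) and 93.0% and 93.5% (skewed). In the skewed case clustering therefore costs 93.0 − 90.2 = 2.8 points at 20×6 and 93.5 − 86.2 = 7.3 points at 10×12.

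**Acceptability curve.** A correct 90% probability of cost-effectiveness would be shown as Φ(1.2816 × √DE): 91.1% (DE 1.10), 92.4% (DE 1.25) or 94.5% (DE 1.55).

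**The case against.** The SAP is silent on practice; it does not exclude it. A mixed model in a cluster-randomised trial may well include practice, and the bootstrap could resample practices without contradicting the text. The imputation list is open-ended, so practice could enter as a variable related to the outcomes. Table 5 lists covariates. Practices are nested within arm, so a practice term would not appear there as a fixed covariate beside arm. The effect can also be small: 5.6% to 6.2% error at ICC 0.01 to 0.02. With 15% drop-out there are 5.1 patients per cluster, so DE is 1.205 and the error at ICC 0.05 is 7.4%, although unequal cluster sizes push the other way.

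Much of this stands. The harm to the primary endpoint is conditional, Table 5 is weak evidence alone, and 10×12 is assumed. It does not rescue the economic analysis. The regression named there addresses only cost-effect correlation. The bootstrap is not stated for the confidence intervals of the effect differences, and plain resampling of practices is little or no better than resampling patients. Random effects and variance methods are SAP content, so the choice should not be left open.

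One may also ask why REML should be preferred when ML with t on K−2 df lies closer to 5%. When the degrees of freedom switch to patient level if the practice variance is estimated as zero, REML gives 4.6% and 4.5% (20×6 and 10×12), against 5.6% and 6.3% for ML.

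**Conclusion.** The concern holds and should be fixed before the main analyses are run. The economic methods as written contain no between-practice variance. The primary and secondary models are unspecified on this point; they are not shown to be wrong. At the plan's own ICC and the smallest mean cluster size its numbers allow, ignoring practice makes standard errors 11% too small and takes a two-sided 5% test to 8.0%; fewer, larger practices make both worse. For the economic results, the probability of cost-effectiveness moves modestly (90% shown as 92.4%), but interval coverage falls to 90–91% at 20×6.

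These sizes assume balanced clusters, one time point and no covariates. The ICC for costs and QALYs is an assumption, with 0.02 to 0.10 giving standard errors 5% to 18% too small at 6 per cluster.

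**What to change.** - **Primary and secondary models:** state a random intercept for practice alongside the within-patient covariance. Base tests and intervals on Satterthwaite or Kenward-Roger degrees of freedom, normally with REML.
- **Economic analysis:** replace plain seemingly unrelated regression with a multilevel bivariate cost-effect model, or specify a two-stage bootstrap by practice within arm with shrinkage correction. Name the small-sample correction, since resampling practices alone is not enough.
- **Imputation:** include practice in the imputation model.

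The cost is SAP wording and modest programming. No new data are needed, because each patient's physiotherapist and practice are known from allocation. Intervals will be wider, and with few practices the tests may be slightly conservative (3.5% to 4.2% for REML with t on K−2 df).
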